In a 1-year, randomized, double-blind, placebo-controlled study in patients with non-transfusion-dependent thalassemia syndromes and iron overload, diarrhea (9.1%), rash (9.1%), and nausea (7.3%) were the most frequent study drug-related adverse events reported by patients receiving 10 mg/kg/day of DFX. Abnormal serum creatinine and creatinine clearance values were reported in 5.5% and 1.8%, respectively, of patients receiving 10 mg/kg/day of DFX. Elevations of liver transaminases greater than 2 times the baseline and 5 times the upper limit of normal were reported in 1.8% of patients treated with 10 mg/kg/day of DFX.

There have been occasional post-marketing reports of leukocytoclastic vasculitis, urticaria, alopecia and hypersensitivity reactions (including anaphylaxis and angioedema).

There have been post-marketing reports (both spontaneous and from clinical trials) of cytopenias including neutropenia, thrombocytopenia, and aggravated anemia in patients treated with DFX. Most of these patients had pre-existing hematological disorders that are

[REDACTED]

frequently associated with bone marrow failure. The relationship of these episodes to treatment with DFX is uncertain.

As with other iron chelator therapies, high frequency hearing loss and lenticular opacities (early cataracts) have been uncommonly observed in patients treated with DFX.

The risk of toxicity of DFX may be increased when inappropriately high doses are prescribed to patients with a low iron burden or with SF levels that are only slightly elevated. Patients with MDS and “other anemias” had slightly more AEs than patients with β -thalassemia, with the most notable differences for gastrointestinal disorders, general disorders, musculoskeletal disorders, respiratory disorders and metabolism disorders.

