2.5 Statistical methods and data analysis

Categorical parameters

Categorical (qualitative) data (e.g., gender, race, etc) will be presented as frequencies and percentages. A missing category for categorical data will be presented where applicable. Unless otherwise noted, percentages will be based on the number of patients in the relevant population or subgroup as the denominator. Categorical variables will be summarized by absolute and relative frequencies where applicable.

Continuous parameters

Continuous (quantitative) data (e.g., age, body weight, etc.) will be summarized by number of patients, mean, standard deviation, median, minimum, and maximum. The lower and upper quartiles may also be used under special circumstances.

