2.9.2.4 To assess iron parameters in patients randomized to EPO alone, DFX+EPO and in patients randomized to EPO alone and switched to DFX+EPO after 12 weeks

This analysis will include patients randomized either to EPO or DFX+EPO at baseline as well as patients who are non-responders to erythroid at week 12 in the EPO group switched to combination therapy. The time-course of serum ferritin and its absolute/relative changes from baseline will be summarized by descriptive statistics by visit and erythroid response. Data will be summarized on FAS.

Note: Patients randomized to EPO and not switching after 12 weeks to EPO+DFX, will consist of only responders.

2.9.2.5 To assess Hb parameters in patients randomized to EPO alone, DFX+EPO and in patients randomized to EPO alone and switched to DFX+EPO after 12 weeks

This analysis will include patients randomized either to EPO or DFX+EPO at baseline as well as patients who are non-responders to erythroid at week 12 in the EPO group switched to combination therapy. The time-course of Hb and its absolute/relative changes from baseline will be summarized by descriptive statistics by visit and erythroid response. Data will be summarized on FAS.

Note: Patients randomized to EPO and not switching after 12 weeks to EPO+DFX, will consist of only responders.

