2.10.3 Laboratory data

All laboratory values will be converted into SI units and the severity grade calculated using the low/normal/high classifications based on laboratory normal ranges and for selected parameters by notable and extended ranges as available in the deferasirox program standards.

Note that, Hemoglobin (g/dL) and Serum Ferritin (ng/mL) are the only exceptions which will be reported in US-units (if appropriate).

Table 2-4 Criteria for clinically notable and extended laboratory ranges

Parameter	Criteria
Absolute neutrophils	<1.5×10 ⁹ /L (extended range <0.5×10 ⁹ /L)
Platelets	<100×10 ⁹ /L (extended range <50×10 ⁹ /L)
ALT/AST	>5×ULN and >2×baseline value (extended range >10×ULN and >2×baseline value)
Serum creatinine	> 33% increase from baseline and >ULN at two consecutive measurements at least 7 days apart
Creatinine clearance	<60 mL/min at two consecutive measurements at least 7 days apart (extended range <40 mL/min)
Urinary total protein/creatinine ratio	>113.1 mg/mmol at two consecutive measurements at least 7 days apart

The frequency of laboratory abnormalities will be displayed by parameter and treatment group. Laboratory data will be summarized by presenting summary statistics of raw values at baseline and changes from baseline (absolute) to worst post-baseline value and by treatment group.

Laboratory data will be summarized by presenting **shift tables** showing baseline versus most extreme post-baseline result by notable range.

Box plots of absolute value will be provided for selected parameters.

Listings of all laboratory data with values flagged corresponding to normal/notable/extended ranges will be provided. The listing of all laboratory values will be provided by planned and actual dose along with the columns for treatment arm to which the patient was randomized and the treatment arm where the patient belongs at the time of the assessment will be provided.

Hematology:

Box plots on absolute value for Hb, neutrophil and platelets corresponding to each visit will be provided.

Absolute change from baseline to worst post-baseline value (the lowest for hematology parameters) will be provided for Hb, neutrophil and platelets.

Absolute change from baseline to last available value at the time of EOT will be provided for Hb, neutrophil and platelets.

Listings will be provided for Hb, platelets and neutrophils as well.

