Only listings will be provided for the parameters: Hematocrit, red blood cell (RBC) count, reticulocyte count, mean corpuscular volume (MCV), White blood cell (WBC) count with differential.

Blood chemistry

Absolute change from baseline to worst post-baseline value (the highest for blood chemistry parameters except creatinine clearance, which the lowest value is considered to be the worst) will be provided for serum ferritin, ALT, AST, total bilirubin, serum creatinine, creatinine clearance and urinary protein/creatinine ratio.

Absolute change from baseline to last available value at the time of EOT will be provided for serum ferritin, ALT, AST, total bilirubin, serum creatinine, creatinine clearance and urinary protein/creatinine ratio.

Shift tables from baseline to post-baseline value will be provided for serum ferritin, ALT, AST, serum creatinine, creatinine clearance and urinary protein/creatinine ratio in the following way:

Serum ferritin - Baseline categories: ≤ 270 ng/mL, $> 270 - 500$ ng/mL, $> 500 - 1650$ ng/mL, > 1650 ng/mL and Missing;

Serum ferritin - Post-baseline categories: ≤ 270 ng/mL, $> 270 - 500$ ng/mL, $> 500 - 1650$ ng/mL, > 1650 ng/mL.

ALT/AST - Baseline categories: \leq ULN, $> ULN - \leq 5 \times ULN$, $> 5 \times ULN - \leq 10 \times ULN$, $> 10 \times ULN$ and Missing;

ALT/AST - Post-baseline categories: \leq ULN, $> ULN - \leq 5 \times ULN$, One value $> 5 \times ULN$, One value $> 10 \times ULN$, Two consecutive values measured at least 7 days apart $> 5 \times ULN$, Two consecutive values measured at least 7 days apart $> 10 \times ULN$, $> 5 \times ULN$ and $2 \times$ Baseline value, $> 10 \times ULN$ and $2 \times$ Baseline value and Missing.

Serum creatinine - Baseline categories: \leq ULN, $>$ ULN and Missing;

Serum creatinine - Post-baseline categories: \leq ULN, One value $>$ ULN, Two values $>$ ULN, Two consecutive values measured at least 7 days apart $>$ ULN, Two consecutive values measured at least 7 days apart $>$ ULN, both $>$ 33% increase from baseline and Missing-

Urinary protein/creatinine ratio – Baseline categories: ≤ 22.62 mg/mmol, $>22.62 - \leq 113.1$ mg/mmol, > 113.1 mg/mmol and Missing; Post-baseline categories: ≤ 113.1 mg/mmol, One value > 113.1 mg/mmol, Two values > 113.1 mg/mmol, Two consecutive values measured at least 7 days apart > 113.1 mg/mmol and Missing.

Creatinine clearance - Classification I:

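### The SAP takes the highest post-baseline serum ferritin as the worst, so the change-to-worst table says little about falling ferritin and no output summarises each patient's lowest value

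*SAP*

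**What the plan says.** SAP 2.10.3, Blood chemistry, plans a table of absolute change from baseline to the worst post-baseline value. Worst is "the highest for blood chemistry parameters except creatinine clearance", for which the lowest counts. Serum ferritin is the first parameter listed under that sentence.

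The same section plans other ferritin outputs:
- a second change table: "Absolute change from baseline to last available value at the time of EOT will be provided for serum ferritin";
- a shift table whose lowest cell is given as "Serum ferritin - Post-baseline categories: ≤ 270 ng/mL", the others being >270-500, >500-1650 and >1650 ng/mL;
- a listing of all ferritin values.

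The general text of 2.10.3 describes shift tables as "showing baseline versus most extreme post-baseline result by notable range". Table 2-4, which holds the notable ranges, has no ferritin row.

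Outside the safety section, SAP 2.9.2.4 plans ferritin by visit on the FAS: "The time-course of serum ferritin and its absolute/relative changes from baseline will be summarized by descriptive statistics by visit and erythroid response". Under SAP 2.5, continuous data "will be summarized by number of patients, mean, standard deviation, median, minimum, and maximum". Protocol 10.5.11.3 also plans descriptive statistics, with minimum and quartiles, for iron-metabolism parameters.

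On risk, Protocol 1.2.1.2 states: "The risk of toxicity of DFX may be increased when inappropriately high doses are prescribed to patients with a low iron burden". It adds patients whose ferritin is only slightly raised.

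**The concern.** For most blood chemistry in the list (ALT, AST, bilirubin, creatinine) a high value is the harmful one, and a highest-value rule is right. Ferritin differs. The study drug is meant to lower it, and inclusion criterion 14 admits patients from 300 ng/mL, or 270 with the 10% tolerance. The patients to whom the Protocol 1.2.1.2 warning applies are those with low or falling ferritin.

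The SAP sets direction by parameter elsewhere. It uses the lowest value for haematology and for creatinine clearance, and in 2.10.4 both highest and lowest for blood pressure, pulse and weight. Ferritin seems to have been left under a default.

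At stake is the reading of one safety table, and perhaps of a second. A reviewer looking for iron depletion in the change-to-worst table would see each patient's least depleted value.

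**Working it through.** The SAP gives no figure to reproduce here. The check applies its rules to assumed ferritin courses.

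**Inputs from the documents.** There are six post-baseline ferritin values: Visits 7, 9, 10, 11, 12 and end of treatment (Protocol Table 7-1), at nominal days 28, 56, 84, 112, 140 and 168 (SAP 4.2.11). The shift cut-offs follow from the entry tolerance: 300 × 0.9 = 270 and 1500 × 1.1 = 1650 ng/mL.

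**Step 1: fixed profiles (assumed, not data).** Each change is the chosen post-baseline value minus baseline.

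| Baseline | Six values | Change to highest | Change to lowest | Change to last | Shift cell by highest / lowest / last |
|---|---|---|---|---|---|
| 400 | 380, 330, 270, 210, 150, 100 | -20 | -300 | -300 | >270-500 / ≤270 / ≤270 |
| 400 | 380, 150, 90, 200, 320, 390 | -10 | -310 | -10 | >270-500 / ≤270 / >270-500 |
| 320 | 265, 240, 200, 150, 110, 80 | -55 | -240 | -240 | ≤270 / ≤270 / ≤270 |
| 600 | 560, 480, 400, 300, 240, 180 | -40 | -420 | -420 | >500-1650 / ≤270 / ≤270 |

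A steady fall is nearly invisible in the change-to-highest column but plain in the change to last. A dip that recovers (row 2) is missed by both. It would appear only in the by-visit summaries and the listing. If the shift table uses the highest value, a patient reaches the ≤270 cell only when all post-baseline values are ≤270.

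**Step 2: how the table can show a rise.** Take baseline 350 and a 5% fall every 4 weeks. The first value on trend is 350 × 0.95 = 332.5. If it is measured 15% above trend it becomes 332.5 × 1.15 = 382, a change of +32. The sixth value on trend is 350 × 0.95⁶ = 257, a change of -93. With the other values on trend, the patient enters the change-to-worst table at +32.

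**Step 3: with random variation.** Model: value k = B × (1 - f)^k × exp(σZ), with k = 1 to 6, Z independent standard normal, σ = 0.15, baseline B taken as fixed, and 200,000 simulated patients. The values of f and σ are assumptions; the documents give neither.

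- Baseline 350, f = 5%: median change +14 to the highest, -115 to the lowest.
- Baseline 350, f = 10%: -20 to the highest, -173 to the lowest.
- Baseline 350, f = 5%, σ = 0.10: -3 to the highest, -104 to the lowest.

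The sign reversal at the median therefore needs a slow fall and the larger variation. The understatement appears in all three cases.

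**Step 4: percentage of patients with a value ≤270 ng/mL (σ = 0.15).**

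| Baseline | Fall per 4 weeks | Lowest ≤270 | Highest ≤270 |
|---|---|---|---|
| 350 | 5% / 10% | 93 / 100 | 0 / 3 |
| 400 | 5% / 10% | 52 / 100 | 0 / 0 |
| 500 | 5% / 10% | 3 / 71 | 0 / 0 |
| 600 | 5% / 10% | 0.07 / 17 | 0 / 0 |
| 800 | 5% / 10% | at most about 0.1 | 0 / 0 |

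The difference in this count is large for patients entering near the floor. It is small from about 600 ng/mL unless ferritin falls fast.

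**The case against.** The strongest reply is that falling ferritin is visible elsewhere. The change to the last value captures a sustained fall. In the simulation from baseline 350, about 63% (5% fall) or 99% (10% fall) of patients have a last value ≤270. The by-visit tables carry a minimum, Protocol 10.5.11.3 adds quartiles, and the listing holds every value. A reader might infer from the highest-value rule that the tables cannot show over-chelation at all. These outputs rule that out. What they leave open is narrower: the end-of-treatment change misses a dip that recovers, a by-visit minimum is one patient's value at one visit, and a listing summarises nothing.

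Second, the highest-value wording sits in the change-to-worst sentence only. It is tempting to say that the shift table also uses the highest ferritin, but the SAP does not say so. It speaks of the most extreme result and gives ferritin no notable range. SAP 1.1 places shells and derivations in Modules 7 and 8, which may settle it. The point on the shift table is therefore an ambiguity.

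Third, 270 ng/mL is an entry tolerance and not a depletion threshold; the documents give none. The percentages in Step 4 should not be read as rates of iron depletion.

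Fourth, Protocol 1.2.1.2 speaks of deferasirox toxicity at inappropriately high doses. It does not name low ferritin as an outcome, and adverse-event, renal and liver tables cover toxicity directly. That is fair, but the passage still makes low ferritin the exposure of interest.

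Fifth, high ferritin also matters in MDS (Protocol 1.1), and some patients on EPO alone never receive a chelator. This supports showing both directions.

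**Conclusion.** The point holds in a limited form. As written, the change-to-worst table takes the uninformative direction for ferritin in a trial of an iron chelator, no output summarises each patient's lowest ferritin, and the shift table's direction for ferritin is unstated. The gap is confined to the change-to-worst table and possibly the shift table. It does not touch the primary endpoint, the sample size or any analysis set.

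The direction of the problem follows from the SAP text alone. Its numerical size rests on assumed rates of fall and within-patient variation and is illustrative only.

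**What to change.** In SAP 2.10.3, take serum ferritin out of the highest-value rule and report absolute change from baseline to both the lowest and the highest post-baseline value, following SAP 2.10.4. State that the ferritin shift table classifies patients by their lowest post-baseline value, with the highest as a second column, and carry this into the table shells and programming specifications.

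The cost is one amended sentence and one extra column in each of the two tables. Ferritin is already measured every four weeks, so no new data are needed. This is a reporting change only and implies no ferritin threshold or dosing rule.

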In conclusion, using the same CrCl limit across the study population will allow for collecting additional renal safety data in this MDS patient population with DFX at the dose of 10 mg/kg/day in combination with EPO in a controlled setting.

- **Change the inclusion criterion of upper limit of Serum Ferritin from 1,000 ng/mL to 1,500 ng/mL (Values within 10% difference above 1500 ng/mL or 10% difference below 300 ng/mL may be accepted at discretion of the investigator if the patient represents the investigational population. However a notification to the study team is required.)**

[figure not shown]
Presently, no data suggests that serum ferritin (SF) levels of 1000 - 1500 ng/mL would change the probability of hematologic response and would impact the homogeneity of the MDS study population.

Public data indicate a high prevalence of red blood cells transfusions 6 month prior to MDS diagnosis based on Hb levels < 10 g/dL in these elderly patients ([Kelaidi 2010](#)).

There is also an increasing understanding of the ineffective erythropoiesis and non-transfusional iron overload in MDS patients ([Fertrin 2014](#)) which explains observed increased SF levels in IPSS lower risk MDS patients at diagnosis even without blood transfusion dependence ([Gattermann 2005](#)). Even though patients must not be transfusion dependent in the present study, they may have received up to 10 RBC transfusions. This transfusional iron together with non-transfusional iron accumulation leads to frequently observed SF levels > 1000 ng/mL in the study population.

The label of DFX allows chelation at SF > 1000 ng/mL. Clinical practice guidelines for treatment of IPSS lower risk MDS patients recommend initiation of supportive care with iron chelation at SF levels > 1000 ng/mL - 2500 ng/mL or if the patient received > 20-50 Units of packed red blood cells ([Gattermann 2008](#)).

In conclusion, the increase of the upper limit of SF for eligibility of this study continues to be in accordance with current clinical practice and corresponds with the target MDS patient population.

Changes to the protocol

Changes to specific sections of the protocol are shown in the track changes version of the protocol using strike through-red font for deletions and red underlined for insertions.

Changes to cover page

- Exjade[®] was deleted.
- Name of new statistician was added to the 'Authors'.

Changes to list of abbreviations

- DT for 'Dispersible tablet' was added.

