5.2 Inclusion criteria

Patients eligible for inclusion in this study have to meet **all** of the following criteria:

1. Written informed consent must be obtained prior to any screening procedures
2. Males and females aged 18 years or more
3. Documented diagnosis of the following:
 - MDS lasting ≥ 3 months and < 3 years
 - Disease must not be secondary to treatment with radiotherapy, chemotherapy, and/or immunotherapy for malignant or autoimmune diseases
4. Patients with low- and Int-1-risk MDS
5. A hemoglobin < 10 g/dL and ≥ 8 g/dL (Values within 5% difference above 10g/dL or 5% difference below 8 g/dL may be accepted at discretion of the investigator if the patient represents the investigational population. However a notification to the study team is required.)
6. History of < 10 RBC transfusions in total and must not be RBC transfusion dependent (A patient is regarded RBC dependent per protocol if the patient received more than 2U RBC/4 weeks at any time during the last 12 week period prior to study entry). Patients must be withdrawn from the study anytime when a RBC transfusion as rescue therapy is clinically indicated.
7. ANC $\geq 500/\text{mm}^3$ (myeloid growth factor support independent)
8. Platelet count $\geq 30,000/\text{mm}^3$ (platelet transfusion independent)
9. Serum creatinine ≤ 1.5 times upper limit of normal (ULN) (mean value of Screening Visit 1 and 2 will be used for eligibility criteria)
10. Creatinine clearance above the concentration limit in locally approved PI. Patients with creatinine clearance between 40 and less than 60 mL/min, who do not present with additional risk factors that may impair renal function, may be eligible at the discretion of the investigator
11. AST and ALT ≤ 2.0 times ULN
12. Serum total bilirubin < 3.0 mg/dL
13. FE/TIBC (TSAT) $\geq 20\%$
14. $300 \text{ ng/mL} < \text{SF} < 1,500 \text{ ng/mL}$ (Values within 10% difference above 1500 ng/mL or 10% difference below 300 ng/mL may be accepted at discretion of the investigator if the patient represents the investigational population. However a notification to the study team is required.)
15. Endogenous EPO levels < 500 units/L

ALLOWED PRIOR CONCURRENT THERAPY:

- Concurrent steroids for adrenal failure, hormones for non-cancer-related conditions (e.g., insulin for diabetes), or intermittent dexamethasone as an antiemetic

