7.2.2.4.3 Urinalysis

Urinalysis samples will be collected at Screening Visits 1 and 2, Randomization Visit 3 and every week during the first four weeks and then every four weeks thereafter. A midstream, second voided morning urine sample will be obtained. Specific gravity, pH, blood, glucose, protein, bilirubin, ketones, and leukocyte esterase will be assessed. Microscopic analysis will be performed only in case of positive dipstick. Dipsticks will be supplied by the central lab.

At Screening Visits 1 and 2, a fresh urine sample (at least 15 ml) will be collected and sent to the central laboratory for urinary protein/creatinine ratio to assess the eligibility of the patient. In addition, urine samples for urinary protein/creatinine ratios will be collected at Randomization Visit 3 and every week during the first four weeks and then every four weeks thereafter, as described in the [Laboratory Manual]. First morning void samples must not be used for this analysis. Significant proteinuria is indicated by a urinary protein/creatinine ratio > 0.1 mg/mg.

For patients who develop proteinuria or a worsening of pre-existing proteinuria (assessed by a dipstick) at any visit, urine samples must be collected and urine protein assessed by the central laboratory.

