Creatinine clearance - Baseline categories: < 40 mL/min, $40 - < 60$ mL/min, $60 - < 90$ mL/min, $90 - < 160$ mL/min, ≥ 160 mL/min and Missing;

Creatinine clearance - Post-baseline categories: Two consecutive values measured at least 7 days apart < 60 mL/min, One value < 60 mL/min, Two consecutive values measured at least 7 days apart $60 - <90$ mL/min, One value $60 - <90$ mL/min, two consecutive values measured at least 7 days apart $90 - < 160$ mL/min, One value $90 - <160$ mL/min, ≥ 160 mL/min and Missing.

Creatinine clearance - Classification II:

Creatinine clearance - Baseline categories: < 40 mL/min, 40 - < 60 mL/min, 60 - < 90 mL/min, 90 - < 160 mL/min, ≥ 160 mL/min and Missing;

Creatinine clearance - Post-baseline categories: Two consecutive values measured at least 7 days apart < 40 mL/min, One value < 40 mL/min, Two consecutive values measured at least 7 days apart 40 - <60 mL/min, One value 40 - <60 mL/min, ≥ 40 mL/min and Missing

Calculation for CrCl:

In the formula below, CrCl denotes creatinine clearance, SCr denotes serum creatinine in μmol/L; age in years will be calculated from date of birth and date of the relevant blood sample. Weight and height will be the last available measurements at the time of the relevant blood sample.

Cockcroft-Gault formula (≥18 years of age),

CrCl (mL/min) =

Male patients: $(140 - \text{age}) \times \text{weight} / (815 \times 0.001 \times \text{SCr})$

Female patients: $(140 - \text{age}) \times \text{weight} \times 0.85 / (815 \times 0.001 \times \text{SCr})$

Note 1: The recalculated creatinine clearance in derived Lab data and standard UNITCONV data:

- Parameter names (PARNAM1C) as 'CRCLSCG' for Cockcroft-Gault formula.
- Preferred (PREUNT1C) and Converted (CNVUNT1C) unit 'mL/min' for Cockcroft Gault formulae.
- Zero Precision (CNVPCS1N) for converted values.

Note 2: For Height and Weight, last available values at the time of assessments should be used. Current age should be derived at the time of assessments.

Listings will also be provided for serum ferritin, ALT, AST, total bilirubin, serum creatinine, creatinine clearance and urinary protein/creatinine ratio.

A listing of all laboratory values will be flagged as appropriate and will be provided along with planned and actual dose (EPO and EPO + DFX). Assessment day relative to first dose of study drug will be included.

All other blood chemistry parameters apart from the ones mentioned above will only be listed.

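### Three defects in the SAP's categorical renal tables: overlapping CrCl categories, a proteinuria table blind below 113.1 mg/mmol, and a notable-CrCl count not split by baseline

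*SAP*

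**What the plan says.** **CrCl shift tables (SAP 2.10.3).** Both classifications use the same non-overlapping baseline categories: <40, 40 to <60, 60 to <90, 90 to <160, ≥160 mL/min and missing. After baseline, Classification I puts every value below 60 into one range and splits the values above it. Classification II begins with "Two consecutive values measured at least 7 days apart < 40 mL/min, One value < 40 mL/min", continues with 40 to <60 (two consecutive values, or one), and ends with "One value 40 - <60 mL/min, ≥ 40 mL/min and Missing". It has no ≥60 category.

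**Notable CrCl (SAP Table 2-4).** The criterion is "<60 mL/min at two consecutive measurements at least 7 days apart (extended range <40 mL/min", with no reference to baseline. The section also plans the frequency of laboratory abnormalities by parameter and treatment group. Inclusion criterion 10 (Protocol 5.2) allows, at the investigator's discretion, "Patients with creatinine clearance between 40 and less than 60 mL/min, who do not present with additional risk factors that may impair renal function".

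**Proteinuria.** Protocol 7.2.2.4.3 states: "Significant proteinuria is indicated by a urinary protein/creatinine ratio > 0.1 mg/mg". SAP Table 2-4 sets the notable cut at ">113.1 mg/mmol at two consecutive measurements at least 7 days apart". In the SAP shift table, baseline has three ranges (up to 22.62, above 22.62 to 113.1, above 113.1 mg/mmol). After baseline there is one range up to 113.1, and the remaining categories only count how often 113.1 was exceeded.

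**The concern.** Serum creatinine rises are a known effect of deferasirox (about 36% of patients, Protocol 1.2.1.2). Among the reasons given in Amendment 3 for a common CrCl limit is that it "will allow for collecting additional renal safety data in this MDS patient population". A reader will therefore look to the renal tables for how many patients worsened, and from what starting point.

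Three features get in the way. One CrCl table gives the same value two places. The proteinuria shift table cannot register worsening below 113.1 mg/mmol, although baseline is divided below that value and the protocol calls a much lower ratio significant. The headline count of notable CrCl also mixes impairment present at entry with decline on treatment.

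**Working it through.** **1. Classification II.** Assigning each whole number from 0 to 199 mL/min to the stated value ranges gives:

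| CrCl (mL/min) | Classification I | Classification II |
|---|---|---|
| 39 | <60 | <40 |
| 40, 50, 59 | <60 | 40 to <60 **and** ≥40 |
| 60, 75 | 60 to <90 | ≥40 |
| 95 | 90 to <160 | ≥40 |
| 160 | ≥160 | ≥40 |

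Classification I has no overlap and no gap. Classification II has no gap, but all values from 40 to 59 fall in two ranges. Under SAP 4.5, percentages are taken over patients with a non-missing post-baseline value. Read literally, they would sum to 100% plus the share whose worst value is 40 to <60: 110% to 140% for assumed shares of 10% to 40%. For example, take 30 patients, 6 with a worst value of 40 to <60 and 24 at 60 or more. The literal reading gives 6 + 30 = 36 entries (120%). A worst-category-first reading gives 6 + 24 = 30 (100%). With ≥60 as the last range, the ranges are <40, 40 to <60 and ≥60, with neither overlap nor gap.

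**2. Proteinuria units.** mg/mmol = mg/mg × creatinine molar mass in g/mol. The documents do not give the molar mass; 113.1 is assumed. Reproducing the SAP's own cuts first:

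- 1.0 mg/mg × 113.1 = 113.1 mg/mmol (the notable cut)
- 0.2 mg/mg × 113.1 = 22.62 mg/mmol (the lower baseline cut)

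Both SAP cuts come out as round numbers, which supports the conversion. The protocol threshold is then 0.1 × 113.1 = 11.31 mg/mmol, and 113.1 / 11.31 = 10.0 (9.998 with 113.12 g/mol). Even the SAP's lower baseline cut is 22.62 / 11.31 = 2 times the protocol value.

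**3. What the protein/creatinine shift table registers.** Take two patients who start at or below 22.62 mg/mmol. One stays there; the other rises to 100. Both land in the same baseline row and the same post-baseline column (≤113.1). Yet 100 / 11.31 is about 8.8 times the protocol's threshold. Any change that stays between 11.31 and 113.1 mg/mmol is lost in the same way.

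**4. Notable CrCl without change.** A patient stable at 50 mL/min meets the <60-twice rule on treatment. The rule is already met before the first dose, because the screening visits are at least 14 days apart (Protocol 7.1.1) and the rule needs 7. Let *s* be the share entering at 40 to <60 and *d* the rate of new decline among the rest. If all of *s* stay below 60, the crude rate is *s* + (1 − *s*) × *d*. The documents give neither input; *d* = 10% is assumed.

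| *s* | crude rate if *d* = 0 | crude rate if *d* = 10% |
|---|---|---|
| 10% | 10% | 0.10 + 0.90 × 0.10 = 19% |
| 20% | 20% | 0.20 + 0.80 × 0.10 = 28% |
| 30% | 30% | 0.30 + 0.70 × 0.10 = 37% |

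These are upper values, since some patients in *s* may not have two consecutive values below 60 on treatment.

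**The case against.** A reader might infer that the plan cannot show renal harm, or that it hides proteinuria. The documents do not support that. SAP 2.10.3 plans absolute change from baseline to the worst and to the last value for serum creatinine, CrCl and the protein/creatinine ratio, and flagged listings of each. A rise to 100 mg/mmol would appear in both. The serum creatinine criterion in Table 2-4 is relative to baseline. The <40 columns of Classification II are untouched by the overlap and match the CrCl threshold in Protocol 6.3.1.2, so a fall from 40 to <60 to below 40 stays visible. Protocol 8.1.3 also brings the creatinine section into the adverse events of special interest. The Amendment 3 sentence sets no renal endpoint.

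On the separate limbs:

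- **Overlap.** It may be a slip for ≥60. The SAP bases shift tables on the most extreme post-baseline result, so a worst-first reading recovers the table, and Classification I shows the patients at 60 and above. This stands as mitigation. But no hierarchy is stated, and Classification II is the only CrCl shift table that separates 40 to <60 from <40.
- **Proteinuria.** Significant and notable are different labels, and Protocol 10.5.11.3 refers analysis to notable and extended ranges without a 0.1 mg/mg cut. So no analysis rule is broken. The tenfold gap is still unexplained, and the collapsed post-baseline category is a weakness by the SAP's own cuts.
- **Notable CrCl.** Absolute limits are also used for neutrophils and platelets, and both CrCl shift tables have a separate 40 to <60 baseline row. An equal share in both arms creates no difference between them. This is why the point is a lesser one.

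The table shells (Module 7) are not available here and may already settle some of this.

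**Conclusion.** The point holds as a weakness of the categorical renal summaries, not as a failure of renal safety monitoring.

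- The Classification II overlap is certain on the text and covers all values from 40 to 59 mL/min.
- The protein/creatinine shift table registers no post-baseline worsening at or below 113.1 mg/mmol; this too is certain on the text.
- The tenfold difference between the protocol and SAP thresholds rests only on the assumed molar mass, which the SAP's own cuts bear out. The documents do not show which threshold is right.
- The inflation of crude notable CrCl is real in direction but unknown in size. A reader might take 28% as an estimate. It is one illustration from assumed inputs, it touches only the crude count, and it does not carry over to the shift tables or the change summaries.

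**What to change.** 1. **Classification II:** replace the last value category, ≥40 mL/min, by ≥60 mL/min.
2. **Protein/creatinine shift table:** use the same cuts after baseline as before (up to 22.62, above 22.62 to 113.1, above 113.1 mg/mmol). The existing single and repeated exceedance categories can stay within the top range.
3. **Proteinuria thresholds:** reconcile Protocol 7.2.2.4.3 with SAP Table 2-4 and state why they differ. If the protocol's threshold is kept, tabulate it (about 11.3 mg/mmol) as a reporting category only; this implies no clinical rule.
4. **Notable CrCl:** present the frequency by baseline CrCl (<60 versus ≥60 mL/min), in line with the shift tables. The Table 2-4 criterion itself need not change.

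The cost is minor work on SAP text and table shells. No new data, visits or laboratory tests are needed.
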